	
if at any visit after Week 8 there is a rise of >50% above the mean of creatinine values from the previous 2 visits, the Investigator should ensure that no reasonable explanation exists for creatinine increase and in particular the following causes:
 
 
• Medications that increase creatinine
 
• Decrease in cardiac output
 
• Obstructive uropathy
 
• Urinary tract infection
 
• Volume depletion
 
 
If addressing these causes does not reduce the creatinine level below the above stated threshold, the investigational medicinal product (IMP) will be stopped for 2 weeks. If at creatinine recheck the patient has returned to below the threshold, then IMP will be restarted at a reduced dose (ie, dose reduced via interactive response technology (IRT) to 200 mg for those randomized to 400 mg; maintained to 200 mg for those randomized to 200 mg, and to placebo for those randomized to placebo). If the creatinine does not return to below the threshold, the IMP will be permanently discontinued but the patient will be asked to continue attending all study visits.
 
Patients will be randomly assigned 1:1:1 to 1 of 3 treatment groups:
 
 
A. Placebo;
 
B. Sotagliflozin 200 mg
 
C. Sotagliflozin 400 mg
 
 
The HbA1c and FPG results will be masked to study sites and patients after randomization and until study end. To prevent partial unblinding, UGE and urine glucose:creatinine ratio (UGCR) results will be also masked to study sites and patients.
 
Additionally, urinalysis by dipstick will not include the measurement of urine glucose. Quantitative urine glucose, albumin, calcium, and creatinine will be measured separately at selected on-site visits by the central laboratory.
 
Early Termination
 
If a patient discontinues treatment with IMP early during the Treatment Period, the patient will have a Premature end of treatment (EOT) Visit, and a Follow-up Visit 4 weeks after the last dose of IMP. In addition, every effort will be made to have all patients return to the site at the time corresponding to their scheduled visits, particularly the Weeks 26 and 52 visits.
 
If the patient does not agree to site visits, they will be contacted by telephone to enquire about safety status, particularly at the time of the initially scheduled end of study.
 
The study design is presented graphically in Section 1.1.

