#### 8.1.1 Dose reduction

The dose maintenance will be handled according to the renal function assessed by the creatinine measurement throughout the study. If at any visit after randomization there is a rise in creatinine level (see details in Section 10.6.2), the Investigator should ensure that no reasonable explanation exists for creatinine increase. Sites will be notified by central laboratory alert if a patient has a >50% increase from Baseline level or >50% above the mean of creatinine values from the last 2 visits, where Baseline level is defined as the mean of creatinine values obtained at Screening and Randomization. The IMP should be stopped for 2 weeks. If at creatinine recheck the patient

has returned to the below threshold then IMP will be restarted at a reduced dose (ie, dose reduced via IRT to 200 mg for patients randomized to 400 mg, maintained to 200 mg for patients randomized to 200 mg, and to placebo for those randomized to placebo). Since IMP received is blinded, patients must return to the site and IRT will be contacted for this IMP re-initiation. Dose reduction can only be obtained at on-site visit by IRT. If the creatinine does not return to below the threshold, the IMP will be permanently discontinued but the patient will be asked to continue attending all study visits.

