### **10.3.1 Temporary treatment discontinuation with investigational medicinal product**

Temporary treatment discontinuation may be considered by the Investigator because of suspected AEs.

Lower extremity complications (such as skin ulcers, infection, osteomyelitis, and gangrene) requiring treatment should lead to temporary discontinuation of IMP.

If at any visit after randomization up to Week 8 there is a rise in creatinine level (ie, >50% increase from baseline level, where baseline level is defined as the mean of creatinine values obtained at Screening and Randomization) or if at any visit after Week 8 there is a rise of >50% above the mean of creatinine values from last 2 visits, the Investigator should ensure that no reasonable explanation exists for creatinine increase.

The IMP should be stopped for 2 weeks.

Re-initiation of treatment with the IMP will be done under close and appropriate clinical/and or laboratory monitoring once the Investigator has considered according to his/her best medical judgment that the responsibility of the IMP in the occurrence of the concerned event was unlikely to be related to the IMP and that the selection criteria for the study are still met (refer to [Section 7.1](#) and [Section 7.2](#)).

If at creatinine recheck the patient has returned to the below threshold then IMP will be restarted at a reduced dose (ie, dose reduced via IRT to 200 mg for those randomized to 400 mg; maintained at 200 mg for those randomized to 200 mg). Since the IMP received is blinded, patients must return to the site and IRT will be contacted for IMP re-initiation.

It is in the interest of the patient to monitor blood glucose during the temporary discontinuation period, therefore regular determination of SMBG is to be performed and documented (see [Section 9.2.1.7](#)).

For all temporary treatment discontinuations, duration should be recorded by the Investigator in the appropriate pages of the e-CRF when considered as confirmed.

Temporary treatment discontinuation decided by the Investigator corresponds to more than 1 dose not administered to the patient.

Use of any other anti-hyperglycemic medication during the time of temporary treatment discontinuation (ie, insulin during a hospitalization) is recorded as concomitant medication with the name and doses recorded in the e-CRF.

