### **11.3.2 Safety population**

Safety analyses will be based on the safety population, defined as all randomized patients who receive at least 1 dose of double-blind IMP (regardless of the amount of treatment administered).

Patients will be analyzed for safety analyses according to the treatment actually received.

In addition:

- Non-randomized but treated patients will not be part of the safety population, but their safety data will be presented separately
- Randomized patients for whom it is unclear whether they took the study medication will be included in the safety population as randomized
- When a patient is exposed to both sotagliflozin and placebo, the patient will be analyzed in the sotagliflozin group according to the treatment kit taken (400 mg or 200 mg, respectively)
- When a patient is exposed to both sotagliflozin 400 mg (treatment kit) and 200 mg (treatment kit), the patient will be analyzed in the sotagliflozin 200 mg group
- Randomized patients will be excluded from the safety population only if there is documented evidence (ie, all study dates recorded as no medication taken) that patients have not taken the study medication

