2.2.1 Randomization and drug dispensing irregularities

Randomization and drug-dispensing irregularities occur whenever:

1. A randomization is not in accordance with the protocol-defined randomization method, such as a) an ineligible patient is randomized, b) a patient is randomized based on an incorrect stratum, c) a patient is randomized twice, or d) in a dynamic randomization scheme the treatment assignment is, in fact, not random, due to a computer program error.

OR

2. A patient is dispensed an IMP kit not allocated by the protocol-defined randomization, such as a) a patient at any time in the study is dispensed a different treatment kit than as randomized (which may or may not contain the correct-as-randomized IMP), or b) a nonrandomized patient is treated with IMP reserved for randomized patients.

Randomization and drug-dispensing irregularities will be monitored throughout the study and reviewed on an ongoing basis.

All randomization and drug-dispensing irregularities will be documented in the clinical study report. If the number of irregularities is large enough to make a tabular summary useful, the irregularities will be categorized and summarized among randomized patients (number and percentages). Nonrandomized, treated patients will be described separately. Listings with additional, relevant details will be provided in appendices.

Randomization and drug-dispensing irregularities to be prospectively identified include but are not limited to:

Randomization and drug allocation irregularities
Kit dispensation without IRT transaction
Erroneous kit dispensation
Kit not available
Randomization by error
Patient randomized twice
Stratification error
Patient switched to another site

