2.3.2 Safety population

Safety analyses will be based on the safety population, defined as all randomized patients who receive at least one dose of double-blind IMP (regardless of the amount of treatment administered), analyzed according to the treatment actually received.

In addition:

- Nonrandomized but treated patients will not be part of the safety population; however, their safety data will be presented separately
- Randomized patients for whom it is unclear whether they took the IMP will be included in the safety population as randomized
- When a patient is exposed to both sotagliflozin and placebo, the patient will be analyzed in the appropriate sotagliflozin group (depending on the treatment kits taken [400 mg or 200 mg])
- When a patient is exposed to both sotagliflozin 400 mg (treatment kits) and 200 mg (treatment kits), the patient will be analyzed in the sotagliflozin 200 mg group
- Randomized patients will be excluded from the safety population only if there is documented evidence (ie, all study dates recorded as no medication taken) that patients have not taken the study treatment. If a patient is dispensed double-blind IMP and is lost to follow-up without any documented evidence, the patient will be considered exposed.

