2.4.3.1 Extent of investigational medicinal product exposure

The extent of IMP exposure will be assessed by the duration of IMP exposure

Duration of IMP exposure is defined as last dose date of double-blind IMP – first dose date of double-blind IMP + 1 day, regardless of unplanned intermittent discontinuations (see [Section 2.5.3](#) for calculation in case of missing or incomplete data).

Duration of IMP exposure will be summarized descriptively as a quantitative variable (number, mean, SD, median, minimum, and maximum) during the 26-week core treatment period and 52-week entire treatment period, respectively. In addition, duration of treatment exposure will also be summarized categorically by numbers and percentages for each of the following categories and cumulatively according to these categories:

- 1 to 28 days,
- 29 to 56 days,
- 57 to 84 days,
- 85 to 126 days,
- 127 to 182 days,
- 183 to 364 days,
- >364 days

Additionally, the cumulative duration of treatment exposure will be provided, defined as the sum of the duration of treatment exposure for all patients, and will be expressed in patient years.

Number and percentages of patients with dose interruption/reduction due to creatinine increase (identified as those who answered Yes to the question “If Actual Total Daily Dose is 0, Was the dose interruption due to creatinine increase per protocol?” in e-CRF “Exposure” page) will be summarized.

Number and percentages of patients by final dose at the end of the treatment will also be presented by each treatment group.

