2.4.5 Analyses of safety data

The summary of safety results will be presented by treatment group. The safety data will be summarized for the 26-week core treatment period and the 52-week entire treatment period separately, unless otherwise specified.

The “observation period” defined in [Section 2.1.4](#) is applicable in all safety analyses for the classification of AEs, determination of treatment-emergent PCSA values and the last on-treatment value for the laboratory, vital sign and ECG.

General common rules

All safety analyses will be performed on the safety population as defined in [Section 2.3.2](#), unless otherwise specified, using the following common rules:

- Safety data in patients who do not belong to the safety population (eg, exposed but not randomized) will be listed separately
- The baseline value (with the exception of serum creatinine and eGFR) is defined as the last available value before the first dose of double-blind IMP. For serum creatinine and eGFR, the baseline value is defined as the average of all values before the first dose of double-blind IMP.
- PCSA values are defined as abnormal values considered medically important by the Sponsor according to predefined criteria/thresholds based on literature review and defined by the Sponsor for clinical laboratory tests, vital signs, and ECG ([Appendix B](#))
- PCSA criteria will determine which patients had at least 1 PCSA during the treatment-emergent adverse event period, taking into account all evaluations performed during the treatment-emergent adverse event period, including nonscheduled or repeated evaluations.

The number of all such patients will be the numerator for the treatment-emergent PCSA percentage.

- The treatment-emergent PCSA denominator by group for a given parameter will be based on the number of patients assessed for that given parameter in the treatment-emergent adverse event period by treatment group on the safety population.
- For laboratory parameters cited in the protocol as efficacy endpoints (including HbA1c and plasma glucose etc), PCSA summaries will not be provided. These parameters will be summarized in efficacy [Section 2.4.4](#).

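### The mixed-kit safety rule makes no exception for the planned dose reduction, so a 400 mg patient who restarts on 200 mg is counted under 200 mg together with the creatinine rise that caused it

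*SAP*

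**What the plan says.** SAP 2.3.2 defines the safety population by treatment actually received and adds that, for anyone "exposed to both sotagliflozin 400 mg (treatment kits) and 200 mg (treatment kits), the patient will be analyzed in the sotagliflozin 200 mg group". Protocol 11.3.2 carries the same rule. Neither names an exception.

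Protocol 8.1.1 makes one such crossover part of the plan. After a creatinine rise of more than 50%, IMP is stopped for 2 weeks. If creatinine is back below the threshold, IMP restarts with the "dose reduced via IRT to 200 mg for patients randomized to 400 mg". The Clinical Trial Summary states the arms side by side: "to 200 mg for those randomized to 400 mg; maintained to 200 mg for those randomized to 200 mg". If creatinine does not recover, IMP is stopped permanently. Protocol 10.3.1 adds conditions for re-initiation: the event must be judged "unlikely to be related to the IMP and that the selection criteria for the study are still met".

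The grouping reaches widely. SAP 2.4.5 states: "All safety analyses will be performed on the safety population as defined in" SAP 2.3.2, unless otherwise specified. SAP 2.4.3 summarizes exposure by actual treatment in the same population. Within that, SAP 2.4.3.1 plans the "Number and percentages of patients with dose interruption/reduction due to creatinine increase" and a table of final dose by treatment group.

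SAP 2.2.1 separately defines a dispensing irregularity: "A patient is dispensed an IMP kit not allocated by the protocol-defined randomization". The mixed-kit rule does not refer to it.

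**The concern.** Membership of the 400 mg safety group depends on a renal outcome after randomization, and the transfer runs one way. A 400 mg patient who recovers and restarts leaves the group and takes along the creatinine rise and everything that happened on 400 mg. A 200 mg patient with the same course stays put.

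Safety of both doses over 52 weeks is a secondary objective, and descriptive tables by dose are its main display. The table most directly about renal tolerability of the dose, the count of creatinine-driven interruptions and reductions, is the one that the rule distorts in a known direction. The final-dose table also loses its purpose. A reduced patient appears under 200 mg with a final dose of 200 mg, so no 400-to-200 mg reduction can be seen in the 400 mg column.

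**Working it through.** **Does the planned restart meet the rule's condition?** Protocol 8.1.1 allows the reduction only through IRT at an on-site visit. Protocol 8.4 says that IRT allocates packages by kit number. A restarted 400 mg patient has therefore taken 400 mg kits and then 200 mg kits, and the rule applies.

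**Inputs.** The plan gives no number of triggers or restarts, so there is no figure of its own to reproduce on this point. Arm size is 92 (Protocol 11.1). That size checks: a difference of 0.5, SD 1.2 and two-sided 0.05 give 80.3% power by noncentral t. All event counts below are assumptions.

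**Formula.** Let x400 and x200 be the true counts, r the number of patients moved, and k the number of those with the event.

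- 400 mg is reported as (x400 − k)/(92 − r), and falls only if k/r > x400/92.
- 200 mg is reported as (x200 + k)/(92 + r), and rises only if k/r > x200/92.

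**Interruption/reduction count.** Every patient moved by a planned reduction is a case, so k = r and both shifts always occur.

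| True 400 vs 200 | Restarts | Reported 400 mg | Reported 200 mg |
|---|---|---|---|
| 5 vs 5 (5.4% each) | 0 | 5/92 = 5.4% | 5/92 = 5.4% |
| 5 vs 5 | 1 | 4/91 = 4.4% | 6/93 = 6.5% |
| 5 vs 5 | 2 | 3/90 = 3.3% | 7/94 = 7.4% |
| 9 vs 5 (9.8%, 5.4%) | 1 | 8/91 = 8.8% | 6/93 = 6.5% |
| 9 vs 5 | 2 | 7/90 = 7.8% | 7/94 = 7.4% |
| 9 vs 5 | 3 | 6/89 = 6.7% | 8/95 = 8.4% |

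With k = r, the order flips when r > 92(x400 − x200)/(184 − x400 − x200). For 9 vs 5 this is 92×4/170 = 2.16, so 3 restarts are needed. For 14 vs 5 it is 92×9/165 = 5.02, so 6 are needed.

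**Creatinine ≥50% row (SAP 2.4.5.4).** Up to Week 8 the trigger is a rise of more than 50% over the mean of the Screening and Randomization values. That is also the SAP baseline unless there are extra pre-dose samples. Such a trigger counts in this row, and again k = r. After Week 8 the comparator is the mean of the last two visits, so a trigger need not be 50% above baseline.

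**Trigger as an adverse event.** If it is reported as one, it moves with the patient in the same way.

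**Other TEAEs.** Take a true 10/92 in each arm with 3 patients moved. If none of them had the event, the result is 10/89 = 11.2% vs 10/95 = 10.5%. If all three had it, 7/89 = 7.9% vs 13/95 = 13.7%. The direction is not fixed.

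**Exposure.** For a patient who completes 52 weeks, reduction at Week w gives w weeks on 400 mg, 2 off and 50 − w on 200 mg. At Week 8 this is 8/2/42; at Week 39 it is 39/2/11. The rule books the 400 mg weeks under 200 mg.

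**The case against.** **The rule may be meant for dispensing errors.** The bullets around it in SAP 2.3.2 cover irregular cases, and a final-dose table by group makes little sense if reduced patients have already left the 400 mg group. This is a fair inference about intent, but the limit is not written in either document, and a programmer following the text would move the patient.

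**Renal events of special interest.** A reader might infer that these too are understated at 400 mg. The definitions do not support that.

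- By the SAP's MDRD formula, a 50% creatinine rise is about a 37% eGFR fall (1.5^−1.154 = 0.626). A 50% fall needs creatinine up about 82% (2^(1/1.154) = 1.82).
- SAP Table 3 requires a decrease lasting at least 30 days without reversible cause, dialysis of at least 90 days, transplant, renal death, or positive adjudication. A moved patient had recovered at recheck and, under Protocol 10.3.1, still met the selection criteria, which exclude eGFR below 15.
- Non-recoverers stay under 400 mg. With 5/92 events per arm and 2 event-free patients moved, the result is 5/90 = 5.6% vs 5/94 = 5.3%, slightly against 400 mg.

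**Pharmacokinetics.** SAP 2.3.3 uses the same grouping, but SAP 2.4.6 names no split by dose, so any effect is uncertain.

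**Existing safeguards.** Safety is descriptive. ESRD, eGFR-decline and albuminuria summaries are ITT, as randomized. Listings show onset dates and action taken with IMP, so reduced patients can be traced. All true, but none of this corrects the by-dose tables.

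**No whole-patient grouping is clean.** Starting-dose grouping puts up to 42 weeks on 200 mg under 400 mg after a Week 8 reduction. That stands and shapes the fix.

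**Conclusion.** The concern holds in a bounded form. As written, the rule conflicts with the planned dose reduction and with the SAP's own final-dose table. It understates 400 mg and overstates 200 mg in three places: the creatinine interruption/reduction count, the ≥50% creatinine row for triggers up to Week 8, and the trigger if reported as an adverse event. Earlier 400 mg events and exposure are also misattributed, but with no fixed direction for other TEAEs or for renal events of special interest.

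The size is unknown. The documents give no restart rate, Protocol 10.3.1 narrows who may restart, and with no restarts the effect is zero. The percentages above rest on assumed counts and on the restart using a 200 mg kit. A reader might infer that the rule reverses the dose order for renal harm. Reversal is arithmetically possible in the trigger count, but it needs enough restarts (3 at 9 vs 5, 6 at 14 vs 5), and nothing in the documents says that this many occurred. The primary endpoint, the testing hierarchy and the ITT renal summaries are not touched.

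**What to change.** Reconcile Protocol 8.1.1 and 11.3.2 with SAP 2.3.2 and 2.4.3.1:

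- Limit the mixed-kit rule to dispensing errors, by reference to the SAP 2.2.1 irregularities.
- Analyse patients with a planned reduction in their randomized (starting) dose group for safety, exposure and laboratory tables.
- Add one display or listing of these patients' events by dose at onset. This covers the small downside that starting-dose grouping counts post-reduction events under 400 mg.
- Enter it in SAP Table 2 as a dated departure from Protocol 11.3.2, made after the first-step analysis that SAP 1.6 says was already run and reported. Show the interruption/reduction count and the ≥50% creatinine row under the original grouping as well.

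The cost is a few lines of SAP text, one extra display and two rows shown in both groupings. No new data are needed. Duplicating all safety tables or re-cutting the PK summaries is not warranted. If no patient restarted on 200 mg, one sentence saying so is enough. The dose-reduction rule itself is not changed.

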2.3.3 PK population

For PK analyses, the PK population is defined as all safety patients who contribute with at least 1 valid plasma concentration of sotagliflozin or its 3-O-glucuronide metabolite. The PK data will be analyzed according to the treatment actually received (see Section 2.3.2).

2.4 STATISTICAL METHODS

2.4.1 Demographics and baseline characteristics

Continuous data will be summarized using the number of observation available, mean, standard deviation (SD), median, minimum, and maximum for each treatment group. Categorical and ordinal data will be summarized using the count and percentage of patients in each treatment group.

Parameters will be summarized on the randomized population analyzed in the treatment group to which they were randomized. Analyses for the safety population will be included in the appendices if the size of the safety population is different (>10%) from the size of that in the primary analysis population for any treatment group.

Parameters described in [Section 2.1.1](#) will be summarized by treatment group and overall (pooled across treatment groups) using descriptive statistics.

P-values on the treatment difference for the demographic and baseline characteristic data will not be calculated.

In general, no specific description of the safety parameters will be provided at baseline. If relevant, the baseline values will be described along with each safety analysis.

In general, no specific description of the efficacy parameters will be provided at baseline. If relevant, the baseline values will be described along with each efficacy analysis.

